ENDPOINT(S)	
Primary endpoint:
 
Phase I part
 
The safety of Isatuximab will be evaluated using DLT criteria described as follows during the Cycle 1.
 
The NCI CTCAE version 4.03 will be used to assess the severity of AE and serious adverse events (SAE). The DLTs will be determined by the Study Committee.
 
Hematologic DLTs are defined as any of the following, attributed to isatuximab:
 
 • Grade 4 neutropenia lasting for ≥ 5 days. • Grade 3 to 4 neutropenia complicated by fever or Microbiologically or radiographically documented infection. • Grade 4 thrombocytopenia lasting for ≥ 5 days. • Thrombocytopenia if required platelet transfusion. • Treatment delay >14 days due to hematologic toxicity. 
Non-hematologic DLTs are defined as any of the following, attributed to isatuximab:
 
 • Grade ≥ 3 non-hematological AE, excluding Grade 3 fatigue, Grade 3 to 4 electrolyte abnormalities, Grade 3 nausea/vomiting/diarrhea if responsive to optimal medical management within 48 hours or allergic reaction/ hypersensitivity attributed to isatuximab. • AE that requires treatment delay for >14 days. • Grade 3 neuropathy will not be considered as a DLT if the patient began therapy with Grade 2 neuropathy at baseline. 
Any other toxicity that the Investigator and the sponsor deem to be dose limiting, regardless of the grade, may also be considered as DLT.
 
Before starting Cohort 2 and Phase II part, all safety data, and the reported potential DLTs will be reviewed to determine their relationship to the IMP. Starting Cohort 2 or Phase II part decisions will be based on the assessment of IMP related DLTs by the Study Committee.

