	
Phase II Part
 
The phase II part of the study aims to evaluate 33-36 patients which include the subjects in Phase I part at the recommended dose level. Given an assumed true ORR of 28%, the null hypothesis ORR \leq10% will be rejected using an exact binomial test at a one-sided alpha of 0.025 with at least 80% power.
 
Analysis populations
 
For both Phase I and Phase II parts of the study, the all treated/safety population will include all patients who have given their informed consent and who have received at least one dose (even incomplete) of Isatuximab. This population is the primary population for the analyses of efficacy and safety parameters. All analyses using this population will be based on the dose level actually received. In the Phase I part, the DLT evaluable population is the subset of patients from the all treated population who have completed the first cycle which consists of 4 administrations of the IMP, or they discontinued the IMP before completion of Cycle 1 for a DLT. The dose escalation will be determined on the DLT evaluable population.
 
The pharmacokinetic population is the subset of patients from the all treated population who have a PK parameter.
 
The activity/efficacy population is the subset of patients from the all treated population who have evaluable data for exploratory analysis.
 
General statistical approach
 
Basically, data from initial dose level and recommended dose level will be analyzed and reported separately. Only the efficacy evaluated in Phase I Cohort 2 and Phase II part is combined for recommended dose level. The separate tables will be presented by phase (when appropriate) unless otherwise noted.
 
Analysis of safety endpoints:
 
IMP related DLTs will be assessed and analyzed on DLT evaluable population.
 
The same analysis below using all treated/safety population will be applied in Phase I and Phase II part.
 
The treatment emergent adverse events (TEAEs) will be coded according to Medical Dictionary for Regulatory Affairs (MedDRA). Adverse events and laboratory abnormalities will be graded according to the NCI-CTCAE v. 4.03. Number (%) of patients experiencing treatment-emergent adverse events by primary system organ class and preferred term will be summarized by CTCAE grade (all grades and Grade \geq3) for the safety population. The same table will be prepared for drug related TEAEs, TEAEs leading to treatment discontinuation, serious TEAEs, TEAEs with fatal outcome, and drug-related SAEs occurred during the post treatment dosing period.
 
Number (%) of patients with laboratory abnormalities (ie, all grades and Grade \geq3) using the worst grade during the on-treatment period will be provided for the safety population.
 
The descriptive statistics of all vital signs' variable will be calculated.
 
Analysis of pharmacokinetic and immune response endpoints:
 
The same analysis will be applied in Phase I and Phase II part.
 
Pharmacokinetic and immune response endpoints and CD38 receptor density will be assessed and analyzed on PK population or activity/efficacy population.

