13.4.4 Analyses of Safety Data

Analyses of data will be based on the all treated/safety population except DLT evaluation.

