13.4.4.1 Dose-limiting toxicities

For the Phase I part of the study, DLTs will be summarized by dose level using DLT evaluable population. Details will be provided (characteristics of DLTs) by patient.

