## **2.3 ANALYSIS POPULATIONS**

### **2.3.1 All treated/safety populations**

The all treated/safety population will include all patients who have given their informed consent and who have received at least one dose (even incomplete) of isatuximab.

This population is the primary population for the analyses of efficacy and safety parameters. All analyses using this population will be based on the treatment actually received.

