##### ***General common rules***

All safety analyses will be performed on the safety population as defined in [Section 2.3.1](#). Unless otherwise specified, the baseline value is defined as the last available value before the first isatuximab administration.

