##### **2.4.5.1 Analyses of adverse events**

###### ***Generalities***

The primary focus of adverse event reporting will be on treatment-emergent adverse events. Pre-treatment and post-treatment adverse events will be described separately.

If an adverse event date/time of onset (occurrence, worsening, or becoming serious) is incomplete, the adverse event will be classified as pre-treatment, treatment-emergent, or post-treatment, according to the cycle number or visit of onset. The algorithm for imputing date of onset will be conservative and will classify an AE as treatment emergent unless there is definitive information to determine it is pretreatment or post-treatment. Details on classification of adverse events with missing or partial onset dates are provided in [Section 2.5](#).

The grade will be taken into account in the summary. For patients with multiple occurrences of the same event during the observation period, the maximum grade is used.

Sorting within tables ensures the same presentation for the set of all adverse events within the observation period (pre-treatment, treatment-emergent, and post-treatment). For that purpose, the table of all treatment-emergent adverse events presented by SOC and PT sorted by the internationally agreed SOC order and decreasing frequency of PTs within SOCs in the highest dose level cohort will define the presentation order for all other tables unless otherwise specified.

The following treatment-emergent adverse event summaries will be generated by dose level for the safety population.

- Overview of treatment-emergent adverse events, summarizing number (%) of patients with any
  - Treatment-emergent adverse event (TEAE)
  - Grade 3-5 TEAE
  - Drug-related TEAE
  - Grade 3-5 drug-related TEAE
  - Serious TEAE
  - Drug-related serious TEAE
  - TEAE leading to death
  - TEAE leading to permanent treatment discontinuation
  - Dose limiting toxicity
  - Infusion associated reaction (excluding symptoms)
  - Grade 3-5 infusion associated reaction (excluding symptoms)
- All TEAEs by primary SOC, HLT, HLT and PT, showing number (%) of patients with at least 1 treatment-emergent adverse event sorted by the SOC internationally agreed order. The other levels (HLT, HLT and PT) will be presented in alphabetical order.
- All TEAEs by grade, primary SOC, and PT, showing the number (%) of patients with at least 1 treatment-emergent adverse event by grade (i.e., all grade,  $\geq$  grade 3).

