- All serious TEAEs by primary SOC and PT, showing the number (%) of patients with at least 1 serious treatment-emergent adverse event.

- All TEAEs related to isatuximab, by primary SOC and PT, showing the number (%) of patients with at least 1 treatment-emergent adverse event related to isatuximab.
- All serious TEAEs related to isatuximab, by primary SOC and PT, showing the number (%) of patients with at least 1 treatment-emergent serious adverse event related to isatuximab.
- All TEAEs leading to treatment discontinuation, by primary SOC and PT, showing the number (%) of patients.
- All TEAEs leading to dose delay or interrupted, by primary SOC and PT, showing the number (%) of patients.
- All TEAEs with a fatal outcome, by primary SOC and PT, showing the number (%) of patients.
- All treatment-emergent DLT by primary SOC and PT, showing the number (%) of patients.
- All treatment-emergent IAR by primary SOC and PT, showing the number (%) of patients.
- IAR-AESI (using the CMQ corresponding to the generic term of infusion related reaction reported by investigator as an AESI):
  - Analysis by patient: number of patients (used as denominator), worst grade by patient, number of episodes by patient (only 1 episode,  $\geq 1$  episode,  $\geq 2$  episodes, .... – an episode corresponds to a unique AE reference ID), first occurrence of IARs, patients with IAR at the first and/or subsequent isatuximab infusion, and number (%) of patients with at least 2 episodes of IARs at the same infusion
  - Analysis by infusion: number of infusions (used as denominator), worst grade by infusion (a patient can have several IAR episodes at the same infusion).
  - Analysis by episode: number of episode (used as denominator), proportion of IARs occurring at each infusion, IAR duration, and day of onset
- IAR-AESI including symptoms as reported by investigator
  - Summary of IAR-AESI by SOC and PT
  - Listing of IAR-AESI

All AEs, AEs related to isatuximab, DLTs, IARs, respiratory AE, neutropenic complications, SAEs, and AEs leading to permanent treatment discontinuation are listed separately.

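### The Phase 1 SAP puts the DLT table by system organ class and preferred term on the safety population and plans no DLT summary on the DLT-evaluable population that the protocol specifies

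*SAP*

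**What the plan says.** **Protocol.** The synopsis makes DLTs the Phase I primary endpoint: "The safety of Isatuximab will be evaluated using DLT criteria described as follows during the Cycle 1". Its statistical part names the population: "IMP related DLTs will be assessed and analyzed on DLT evaluable population". Section 13.4.4 sets the general rule and the exception together: "Analyses of data will be based on the all treated/safety population except DLT evaluation". Section 13.4.4.1 repeats the requirement: "DLTs will be summarized by dose level using DLT evaluable population". Section 13.4.4.2 also includes a DLT line in the overview of treatment-emergent events, where percentages are taken over all treated patients.

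**Phase 1 SAP.** Section 2.4.5 states: "All safety analyses will be performed on the safety population as defined in" Section 2.3.1, which covers everyone "who have received at least one dose (even incomplete) of isatuximab". No exception for DLTs follows. Section 2.4.5.1 then introduces its tables: "The following treatment-emergent adverse event summaries will be generated by dose level for the safety population". Two items on that list concern DLTs: a row in the overview, and a separate table described as "All treatment-emergent DLT by primary SOC and PT, showing the number (%) of patients". Neither is given another denominator. Section 2.3.2 defines the DLT-evaluable population as patients who received all four Cycle 1 infusions or stopped earlier because of a DLT, with those excluded being replaced. Section 2.2 counts this population in the disposition table. No analysis in the SAP uses it.

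**The concern.** The protocol singles out DLTs as the one safety analysis not done on all treated patients, and the SAP removes that distinction. The two populations can differ. A patient who received one infusion and left Cycle 1 early for a reason other than a DLT is replaced for DLT purposes but stays in the safety population. A programmer following the SAP would therefore produce the DLT table with a denominator, and possibly a numerator, that the protocol did not intend.

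At stake is the reported result for the Phase I primary endpoint. The study report could show a DLT percentage that does not match the one on which the cohort decision was made, with no table giving the protocol's version beside it.

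**Working it through.** **Step 1: does the SAP assign the DLT-evaluable population to any analysis?** Where the Phase 1 SAP wants a population other than the safety population, it says so. Section 2.3.3 attaches the pharmacokinetic parameter analysis to its own population, and Section 2.4.6.3 names the ADA-evaluable population for immunogenicity. Nothing comparable appears for DLTs. In 2.4.5, the phrase allowing for other specifications qualifies the definition of baseline, not the choice of population. A DLT-evaluable denominator therefore cannot be read into the text.

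**Step 2: which DLT item departs from the protocol?**

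| Phase 1 SAP item | SAP population | Protocol population | Agreement |
|---|---|---|---|
| DLT row in overview (2.4.5.1) | Safety | All treated (13.4.4.2) | Yes |
| DLT table by system organ class and preferred term (2.4.5.1) | Safety | DLT-evaluable (13.4.4, 13.4.4.1) | No |
| DLT summary on DLT-evaluable patients | Not planned | Required (synopsis, 13.4.4.1) | No |

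**Step 3: the protocol's own figure.** Section 6.3 sets the maximum administered dose at 2 or more DLTs in at most 6 patients, given as at least 33%. 2/6 = 33.3% reproduces it; 1/6 = 16.7% lies below.

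**Step 4: size of the difference.** Let d be the DLTs among e evaluable patients, k the number treated but not evaluable, and m the number of those k who had a DLT.

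- Protocol rate = d/e
- SAP rate = (d + m)/(e + k)

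The documents do not give k or m. I assume k from 0 to 3.

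| d/e | k | m | Protocol rate | SAP rate |
|---|---|---|---|---|
| 2/6 | 0 | 0 | 33.3% | 2/6 = 33.3% |
| 2/6 | 1 | 0 | 33.3% | 2/7 = 28.6% |
| 2/6 | 2 | 0 | 33.3% | 2/8 = 25.0% |
| 2/6 | 3 | 0 | 33.3% | 2/9 = 22.2% |
| 1/6 | 1 | 0 | 16.7% | 1/7 = 14.3% |
| 1/6 | 1 | 1 | 16.7% | 2/7 = 28.6% |
| 0/3 | 1 | 0 | 0% | 0/4 = 0% |

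For k of at least 1, the SAP rate is lower when m/k < d/e and higher when m/k > d/e, so the direction is not fixed. The case m = 1 can arise under Section 2.3.2: a patient with a DLT who stopped before the fourth infusion for another reason, such as progression, or whose data are too incomplete for DLT evaluation, is not evaluable but remains in the safety population.

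**The case against.** The strongest reply has four parts.

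- **The overview row follows the protocol.** This stands. Protocol 13.4.4.2 lists DLT in its overview on an all-treated denominator, so moving that SAP row to another population would create a new departure.
- **Escalation is untouched.** This stands. A reader might infer that a table showing 2/7 could undercut a decision that the maximum administered dose was reached. The documents do not support that. The synopsis bases escalation on the DLT-evaluable population, Sections 6.2.2 and 9.1.1 state the rule in counts, and the Study Committee reviews the events. Two DLTs still appear as two in the table.
- **The effect is conditional and has no fixed sign.** This stands. A reader might infer that replaced patients systematically dilute the DLT rate. That holds only if there is a non-evaluable patient and a DLT in the same cohort and the excluded patients had no DLT, or proportionately fewer.
- **The gap can be bridged by hand.** This stands in part. The SAP is to be read with the protocol, DLTs are listed separately, the evaluable count appears in disposition, and only 6 to 12 evaluable patients are expected. A careful reader could rebuild the rate. But reading the two documents together exposes the conflict without resolving it: the SAP states a population for this table and the protocol states a different one.

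The SAP's change table (Section 1.6, Table 2) does not mention the difference. It logs changes made to the SAP rather than departures from the protocol, so I draw nothing from its silence.

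**Conclusion.** The point holds in a narrow form. For the DLT table by system organ class and preferred term, the Phase 1 SAP states a population that conflicts with the protocol, and the DLT summary required by protocol 13.4.4.1 is absent. This is a contradiction on the Phase I primary endpoint, not merely missing detail, and it should be corrected.

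Its numerical effect is limited. It is zero if no treated patient is replaced or no DLT occurs in the cohort. With one non-evaluable patient beside six evaluable ones, the reported figure can fall from 33.3% to 28.6%, below the protocol's 33% mark, or rise from 16.7% to 28.6%. These examples rest on assumed replacement counts. The documents support neither a claim of consistent downward bias nor any claim that dose escalation was compromised.

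**What to change.** - In Phase 1 SAP 2.4.5, add to the safety-population rule an exception for DLT evaluation, matching protocol 13.4.4.
- In 2.4.5.1, state that DLTs are summarised by dose level, including the table by system organ class and preferred term, with the DLT-evaluable population of 2.3.2 as denominator, citing protocol 13.4.4.1.
- Keep the DLT row of the overview on all treated patients, in line with protocol 13.4.4.2, and label it as such.
- Keep events in non-evaluable patients in the treatment-emergent adverse event tables and in the DLT listing, so that nothing is lost from view.

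The cost is a few words of SAP text, the denominator (and, if an excluded patient had a DLT, the numerator) of one table, and a row label. No new data are needed. The reported DLT percentage may go up, go down or stay the same.

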#### **2.4.5.2 Deaths**

Number (%) of patients who died by study period (on-treatment and post-treatment) and within 60 days from first dose of study treatment, and cause of death will be summarized. All deaths with relevant information (which are study period, cause of death, death date, etc.) will be listed.

#### **2.4.5.3 Analyses of laboratory variables**

The summary statistics (including number, mean, median, standard deviation, minimum, and maximum) of all laboratory tests will be calculated for each planned visit (for cycle 1 to cycle 3) by dose level cohort.

Each laboratory test result will be graded by NCI CTCAE (version 4.03), when applicable. Sponsor generic ranges are used for the grading of laboratory results, otherwise site ranges are used. For patients with multiple occurrences of the same laboratory variable during the on-treatment period, the maximum grade (worst) per patient will be used. The number (%) of patients with abnormal laboratory tests at baseline and during the on-treatment period will be presented by all grades and each grade. At baseline, the last available value before or on the date of first study treatment administration (excluding repeated tests) will be used.

All laboratory variables will be listed.

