6.6.2 Management of Potential Tumor Lysis Syndrome

General guidelines for the management of the tumor lysis syndrome are provided in [Table 4](#).

Table 4 - Tumor lysis syndrome management

Symptom	Recommended Action
Laboratory Tumor Lysis Syndrome (LTLS): 
• ≥ 2 simultaneous abnormalities within 3 days prior to and up to 7 days after start of treatment• Uric acid >8 mg/dL (>475.8 μmol/L)• Potassium >6.0 mmol/L• Phosphorus >4.5 mg/dL (>1.45 mmol/L) Corrected calcium <7.0 mg/dL (<1.75 mmol/L) or ionized calcium <1.12 mg/dL (<0.3 mmol/L) ^a	Omit isatuximab until all serum chemistries have resolved Ensure normal hydration; correct laboratory abnormalities, fluid overload, electrolyte or acid-based deviations Monitor TLS complications including renal functions Refer to "serious adverse drug reaction countermeasure manual" for TLS treatment ^b . Reinstitute isatuximab treatment at full doses after resolution
Clinical TLS (CTLS): meeting criteria for LTLS in addition to one of the following complications, 
• Acute kidney injury: increase in the serum creatinine level of 0.3 mg/dL (26.5 μmol/L) or the presence of oliguria, defined as an average urine output of <0.5 mL/kg/hr for 6 hrs.• Seizures, cardiac dysrhythmia, neuromuscular irritability (tetany, paresthesias, muscle twitching, carpopedal spasm, Trousseau's sign, Chvostek's sign, laryngospasm, bronchospasm), hypotension, or heart failure probably or definitely caused by hypocalcemia• Dysrhythmia probably or definitely caused by hyperkaliemia	

a The corrected calcium level in milligrams per deciliter = measured calcium level in milligrams per deciliter + $0.8 \times (4 \text{-albumin in grams per deciliter})$

b Serious adverse drug reaction countermeasure manual for TLS: <http://www.mhlw.go.jp/topics/2006/11/dl/tp1122-1e17.pdf>
MHLW site: http://www.mhlw.go.jp/stf/seisakunitsuite/bunya/kenkou_iryou/iyakuhin/topics/tp061122-1.html

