9.1.1 Dose-limiting Toxicities in Phase I part

For the purposes of dose escalation and determination of tolerability of recommended dose, only DLTs that occur during the first cycle of treatment will be considered for decisions regarding dose escalation and phase transition. The standard duration of DLT evaluation period is 28 days however treatment delay up to 14 days is allowed in the first cycle. The detailed DLT evaluability is defined in [Section 13.3.2](#).

Hematologic DLTs are defined as any of the following, attributed to isatuximab:

- Grade 4 neutropenia lasting for ≥ 5 days.
- Grade 3 to 4 neutropenia complicated by fever
OR
Microbiologically or radiographically documented infection.
- Grade 4 thrombocytopenia lasting for ≥ 5 days.
- Thrombocytopenia if required platelet transfusion.
- Treatment delay > 14 days due to hematologic toxicity.

Non-hematologic DLTs are defined as any of the following, attributed to isatuximab:

- Grade ≥ 3 non-hematological AE, excluding Grade 3 fatigue, Grade 3 to 4 electrolyte abnormalities, Grade 3 nausea/vomiting/diarrhea if responsive to optimal medical management within 48 hours or allergic reaction/ hypersensitivity attributed to isatuximab.
- AE that requires treatment delay for > 14 days.
- Grade 3 neuropathy will not be considered as a DLT if the patient began therapy with Grade 2 neuropathy at baseline.

Any other toxicity that the Investigator and the sponsor deem to be dose limiting, regardless of the grade, may also be considered as DLT.

DLTs will be handled as well as Adverse Event of Special Interest (AESI) (See [Section 10.5.5](#)). As such, the investigators will be required to report them to Sanofi within 24 hours of investigator awareness of each event.

Before starting Cohort 2 and Phase II part, all safety data, and the reported potential DLTs will be reviewed to determine their relationship to the IMP. Starting Cohort 2 or Phase II part decisions will be based on the assessment of IMP related DLTs by the Study Committee.

Dose escalation will be stopped if $\geq 33\%$ (≥ 2 in up to 6 patients) of patients experienced an IMP related DLT observed during the first cycles of treatment (4 weeks), according to the definition of MAD.

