#### **2.1.4.3 Laboratory safety variables**

Clinical laboratory data consists of blood analysis, including hematology, clinical chemistry, and urinalysis. Clinical laboratory values will be converted into standard international units and international units that will be used in all listings and tables.

Blood samples for clinical laboratories will be taken as defined in the study flow charts and as clinically indicated. The laboratory parameters will be classified as follows:

- Hematology
  - **Red blood cells and platelets and coagulation:** hemoglobin, hematocrit, mean corpuscular volume, red blood cell count, platelet count, prothrombin time (expressed as international normalized ratio), activated partial thromboplastin time
  - **White blood cells:** white blood cell count, neutrophils, lymphocytes, monocytes, basophils, eosinophils
- Clinical chemistry
  - **Metabolism:** glucose, total protein, albumin
  - **Electrolytes:** sodium, potassium, chloride, calcium, corrected serum calcium, phosphate, magnesium
  - **Renal function:** creatinine, blood urea nitrogen, uric acid, e-GFR (revised equations for e-GFR in Japanese)
  - **Liver function:** alanine aminotransferase, aspartate aminotransferase, alkaline phosphatase, lactate dehydrogenase, total and conjugated (direct) bilirubin
  - **Pregnancy test:** serum  $\beta$ -human chorionic gonadotropin (all female patients)
  - **Hepatitis screen:** hepatitis B surface antigen (HBs-Ag, HBc-Ab, and HBs-Ab), HBV-DNA, anti-hepatitis-C antibody (HCV-Ab)

Urine samples will be collected as follows:

- **Urinalysis** – quantitative: pH, leukocytes, erythrocytes and specific gravity
- **Urinalysis** – qualitative: blood, ketones, bilirubin, leucocytes, nitrates, proteins and glucose

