**Table 8 - Biochemistry parameters**

LBTEST	LBSTRESU	LBGNNRLO - LBGNNRHI
Albumin	g/L	35 - 55
Blood Urea Nitrogen (BUN)	mmol/L	3,6 – 7,1
Corectected calcium	mmol/L	2,2 - 2,6
Chloride	mmol/L	80 - 115
Glucose	mmol/L	3,9 - 7
Bicarbonate (HCO3)	mmol/L	22 – 29
Potassium	mmol/L	3,5 – 5
Magnesium	mmol/L	0,8 - 1,2
Sodium	mmol/L	136 – 145
Phosphate	mmol/L	1 - 1,4
Protein	g/L	55 – 80
Urea	mmol/L	3,6 - 7,1

ted14095-p2-16-1-9-sap

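### The Phase 1 and Phase 2 SAPs use different sponsor reference ranges for sodium and BUN under the same grading rule, without a stated reason, so low-grade laboratory abnormality counts are not comparable between the two parts.

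*SAP*

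**What the plan says.** Section 2.4.5.3 of each SAP grades laboratory tests by NCI-CTCAE 4.03 where applicable, with the same precedence: "Sponsor generic ranges are used for the grading of laboratory results, otherwise site ranges are used". The resulting table is also the same in both: "The number (%) of patients with abnormal laboratory tests at baseline and during the on-treatment period will be presented by all grades and each grade".

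The ranges are in Phase 1 SAP Appendix B, Table 7 (biochemistry) and Phase 2 SAP Appendix A, Table 8. Both use mmol/L for sodium, BUN, urea and calcium.

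- **Sodium:** 129-160 in Phase 1, 136-145 in Phase 2.
- **BUN:** no lower limit and an upper limit of 17 in Phase 1; 3.6-7.1 in Phase 2.
- **Urea:** 3.6-7.1 in both.
- **Calcium:** 2.2-2.6 in both, but the row is labelled as plain calcium in Phase 1 and as "Corectected calcium" (sic) in Phase 2.

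Section 2.1.4.3 of both SAPs names measured and corrected calcium as separate variables: "calcium, corrected serum calcium, phosphate, magnesium".

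The Phase 1 SAP's own change history (Table 2) does not mention reference ranges. Section 1.6 of the Phase 2 SAP records no changes because it is a first version.

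**The concern.** A sponsor generic range should be one range. Here the same sponsor, study and precedence rule give two. Because the generic range takes priority, a site's own sodium range cannot correct whichever table is wrong.

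The graded table matters because Protocol 10.5.1 and 10.5.8 make a laboratory abnormality an adverse event only in limited cases: an effect on study treatment, a seriousness criterion, or AESI status. Other abnormalities are counted only in the graded laboratory table. Safety and tolerability is the Phase I primary objective (Protocol 5.1). A reader will naturally set Cohort 2 beside the Phase II part if both receive the same dose. With 3 to 6 evaluable patients in a cohort, reclassifying one patient moves an abnormality rate by 1/6 to 1/3, that is, by 17 to 33 percentage points.

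**Working it through.** The plan gives no figure of its own to reproduce. The check is a row-by-row comparison, followed by the protocol's calcium formula.

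**Step 1: compare the tables.** Of the 12 biochemistry rows, 10 have identical numeric limits. Sodium and BUN differ.

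| Row (mmol/L) | Phase 1 Table 7 | Phase 2 Table 8 | In range in Phase 1, out of range in Phase 2 |
|---|---|---|---|
| Sodium | 129-160 | 136-145 | 129-135 and 146-160 |
| BUN | up to 17 | 3.6-7.1 | below 3.6; above 7.1 up to 17 |
| Urea | 3.6-7.1 | 3.6-7.1 | none |
| Calcium (label differs) | 2.2-2.6 | 2.2-2.6 | none from the limits |

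**Step 2: size of the differences.**
- Sodium band width: 160 − 129 = 31 mmol/L in Phase 1 and 145 − 136 = 9 in Phase 2. The whole-number values that change status are 7 low (129 to 135) plus 15 high (146 to 160), 22 in all.
- BUN upper limits: 17 / 7.1 = 2.4-fold.
- Within Phase 1 Table 7, BUN (17) and urea (7.1) have different upper limits in the same unit. Phase 2 Table 8 gives both rows 3.6-7.1. This points to an error or unit mismatch in the Phase 1 BUN row. No such internal evidence exists for sodium.

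**Step 3: calcium.** The footnote to Protocol Table 4 (section 6.6.2) begins "The corrected calcium level in milligrams per deciliter = measured calcium level in milligrams per deciliter" and adds 0.8 × (4 − albumin in g/dL). The same table equates 7.0 mg/dL with 1.75 mmol/L, so 1 mg/dL is 1.75 / 7.0 = 0.25 mmol/L. At an albumin of 3.0 g/dL (an illustrative value):
- shift = 0.8 × (4 − 3.0) = 0.8 mg/dL = 0.20 mmol/L;
- measured values above 2.4 and up to 2.6 look normal but correct to above 2.6;
- measured values from 2.0 to below 2.2 look low but correct to 2.2 or more.

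Uncorrected calcium therefore misclassifies in both directions. Corrected calcium has no generic range in Phase 1 Table 7, so by the quoted rule it falls to site ranges in Phase 1, while Phase 2 grades it against 2.2-2.6.

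**Step 4: hematocrit.** The hematology tables of both SAPs give lower limits of 0.41 (male) and 0.36 (female) with the unit shown as %. These figures make sense as fractions. The slip is the same in both SAPs, so it does not cause a difference between phases.

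**The case against.** The strongest reply is that little depends on these tables.

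- **Nothing is concealed.** Phase 1 SAP 2.4.5.3 states "All laboratory variables will be listed" and also plans summary statistics, including minimum and maximum, by planned visit for cycles 1 to 3. With 6 to 12 evaluable patients, the listing can be read patient by patient. This stands: the problem is a missing count in the graded table, not missing data.
- **No Phase I decision is shown to turn on the ranges.** Non-hematologic DLTs exclude "Grade 3 to 4 electrolyte abnormalities", and Protocol 9.1.1 says "Starting Cohort 2 or Phase II part decisions will be based on the assessment of IMP related DLTs by the Study Committee". This stands too.
- **The grade effect is only partly known.** The documents do not reproduce the CTCAE cut-offs. A grade defined by a fixed value would not move with the range limit, and grading applies only where applicable, so BUN may not be graded at all. This limits the claim to flags and grades that depend on the range limit.
- **Pooling is not planned.** The protocol's statistical summary and section 13.4 combine the parts for efficacy only. Comparability is affected; a pooled safety analysis is not.

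None of this explains why two tables described as sponsor generic ranges disagree under the same rule.

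**Conclusion.** The sodium and BUN ranges conflict and the difference is unexplained. Followed as written, the two SAPs can classify the same sodium result (129-135 or 146-160 mmol/L), or the same BUN result above 7.1 and up to 17 mmol/L, differently. Low-grade abnormality counts for these tests are therefore not comparable between parts. The consequence is minor to moderate because it is confined to descriptive safety tables, and it rests on the assumption that at least some flags or grades use the range limit as their boundary.

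A reader might infer more, and four stronger readings are not supported:
- **That abnormal Phase I values are reported as normal, or that the Phase I safety conclusion is undermined.** Raw values remain visible, and escalation rests on DLT review.
- **That calcium is a third range conflict.** The limits match; only the label and the handling of corrected calcium differ.
- **That the Phase 2 limits are proven right.** The documents prove the disagreement and point to a fault in the Phase 1 BUN row. They do not establish which sodium range is correct.
- **That a known share of patients is affected.** The documents give no sodium distribution. If one assumes a mean of 138 to 140, between- and within-patient SDs of 1.5 to 2 each, and eight samples per patient, simulation gives 9% to 55% of patients with a value below 136 and at most 0.3% below 129. That spread comes wholly from the assumptions, so the conclusion does not use it.

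**What to change.** 1. Reconcile the sodium and BUN rows to one sourced sponsor table used in both SAPs. Use the Phase 2 limits (sodium 136-145, BUN 3.6-7.1 mmol/L) unless the sponsor documents another source.
2. In Phase 1 Table 7, apply 2.2-2.6 mmol/L to albumin-corrected calcium, as in Phase 2.
3. In both hematology tables, make the hematocrit unit agree with its limits: 0.41 and 0.36 as a fraction, or 41 and 36 as %.
4. Rerun the Phase I laboratory grading and record the change in the SAP history.

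The cost is a few appendix corrections and one program rerun. The downside is that more low-grade abnormalities may be reported in Phase I.
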